The study population will include adults who were fully vaccinated against SARS-CoV-2 virus (i.e., two doses of Pfizer or Moderna vaccines or one dose of the J&J vaccine), and have received a Roche SARS-CoV-2 Semi-Quant Spike Ig Ab test at least 3 weeks after full vaccination as part of their usual clinical care at AHF Midtown Manhattan Healthcare Center.

Incidence rates of COVID vaccine response levels (i.e., adequate, low, non-response) will be estimated using univariate Poisson regression, overall and by vaccine type. Among individuals with at least two antibody measurements, rates of antibody levels decay will be estimated using univariate linear regression, overall and stratified by HIV status, vaccine type and baseline CD4 cell count. In the sub-population of individuals who received a COVID vaccine booster, vaccination and antibody response will be characterized at least 3 weeks after the booster is received. Univariate linear regression will be used to estimate rates of antibody levels decay, among individuals with at least two antibody measurements, including one after the booster dose. Rates of response decay will be produced overall, and stratified by HIV status, booster type and baseline CD4 cell count.

2. Introduction

BACKGROUND

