The standardization of the data to common terms and application of the Evidian knowledge base are key process steps in gathering data from multiple heterogeneous EHR systems and databases from many locations into a single, homogenous OPERA database for conducting research and commercial analyses. The patient health data gathered, classified and aggregated includes complete medical history & social history, visit dates, vital signs, lab orders and results, medications, problems & diagnoses, and procedures.

Evidian has developed rigorous data management processes that include both automated and manual quality checks. Data quality methods include common techniques such as:

- Detection and reporting of outliers that lead to correction, acceptance, or exclusion of observations; these can include a medical review.
- Detection of potentially missing data (e.g., a patient taking ART medications with no history of HIV infection to determine whether the use was prophylactic or treatment for infection diagnosed elsewhere).
- Data completion using multiple observations and sources (e.g., using diagnoses codes, free text, past medical history, etc. to determine if patient is naive to HIV therapy).
- Detection of observations that are known to be (or likely to be) mutually exclusive for a patient (e.g., record of medications that are typically not administered concurrently).

5. Study Population

Individuals presenting for care at AHF Midtown Manhattan Healthcare Center and followed through their electronic health records in the OPERA Observational Database.

INCLUSION CRITERIA

Patients who were:

1. Cared for at AHF Midtown Manhattan Healthcare Center and followed in the OPERA observational database
2. Active in care in the last 24 months
3. Fully vaccinated against SARS-CoV-2 virus, implemented as 21 days after the second Pfizer or Moderna injections, 21 days after the one J&J injection
4. Received a Roche SARS-CoV-2 Semi-Quant Spike Ig AB test after full vaccination as usual clinical care
5. ≥ 18 years of age at vaccination

EXCLUSION CRITERIA

Patients who were:

1. Unvaccinated or partially vaccinated against SARS-CoV-2 virus
2. Never tested with a SARS-CoV-2 Semi-Quant Total AB test after full vaccination

6. Study Design

OVERVIEW OF STUDY DESIGN

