The design for this study is an observational cohort study utilizing prospectively collected electronic medical record (EMR) data from usual clinical care at AHF Midtown Manhattan Healthcare Center, obtained from the OPERA® Observational Database.

The study population will consist of adults vaccinated against SARS-CoV-2 virus receiving the Roche SARS-CoV-2 Semi-Quant Spike Ig AB test as part of their usual clinical care. These individuals will be followed from vaccination until study end.

EXPOSURES OF INTEREST

Initial vaccination with Pfizer, Moderna, and J&J COVID vaccines, booster vaccination with Pfizer, Moderna, and J&J vaccines, and concordant boosting versus discordant boosting

SUBGROUPS OF INTEREST

HIV-positive versus HIV-negative patients, individuals with at least 2 measurements of antibody levels, and boosted individuals are the subgroups of interest.

STUDY ENDPOINTS

Endpoints for both the primary and secondary objectives are non-responders and low responders and rates of decline of SARS-CoV-2 antibodies

- Non-response will be defined as: 0 to <50 U/mL
- Low response will be defined as: ≥ 51 to ≤ 250 U/mL
- Adequate response will be defined as: >251 U/mL

Roche's Elecsys semi-quantitative spike Ab Ig assay is a commercially available assay that can potentially be utilized to help guide the need for an additional vaccination dose based upon the levels of antibodies that have been previously clinically correlated with neutralizing antibodies. As part of routine care, Ab Ig assays were performed for some patients at the AHF Midtown Manhattan Healthcare Center and results were recorded in their EHR.

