To normalize across different neutralization assays utilized in phase 3 studies of various COVID-19 vaccines, Khoury, et al., estimated that a 50% protective neutralization level equivalent to 20% of the mean titer in the convalescent subjects equates to a measured in vitro neutralization titer of between 1:10 and 1:30 was approximated at 54 international units IU/ml (95% CI 30–96 IU/ml) against wild-type CoV-19 infection.^{xx} During the period of COVID-19 infection where the Delta virus predominated, a quantitative spike Ab's >250 IU/mL was deemed adequate, based on studies that show that an antibody titer of 4-6x wild-type SARS-CoV-2 were required to effectively neutralize Delta viral strains.^{xxi,xxii, xxiii} We thus utilized a threshold level of >250 (5x wild-type ab levels) IU/mL as an adequate vaccine response against circulating Delta virus post last vaccination recommended in a series, a level of <50 IU/mL as a non-responsive post vaccination titer (inadequate for even wild-type Co-V-2 infection), and levels between (50-250 IU/mL) as a low vaccine response. Non and low-responders who had Co-V-2 Spike Ig levels that were inadequate based on the correlation of Spike Ig levels and neutralizing ab correlations relative to the predominant circulating viral strains were offered optional booster vaccinations with subsequent antibody response measurement post vaccination as standard of care. These recommendations are the current one's implemented during the Delta Co-V-2 19 outbreak by the Ministry of Solidarity and Health of France and the COVID Guidelines group in Geneva, where 260 IU/mL and 300 IU/mL, respectively, are considered gray zones of antibody protection against the Delta virus and where booster vaccinations are recommended for consideration.^{xxiv, xxv}

STUDY COVARIATES

Covariates of interest include: age, sex, race, ethnicity, HIV status, region, payer, immunosuppressive conditions, CD4 cell count, comorbid conditions, BMI. This information will be obtained from each patient's electronic health records.

7. Statistical Analysis

ANALYSIS OF DEMOGRAPHICS/BASELINE CHARACTERISTICS

Demographic and clinical characteristics will be summarized in the overall population using medians with interquartile ranges (IQR) for continuous variables and frequencies with proportions for categorical variables.

ANALYSIS OF PRIMARY OBJECTIVES

Objective #1: COVID-19 vaccine non-response and low response as measured by antibody test by HIV status

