Records will be examined retrospectively to determine which patients, both HIV-positive and negative, were non-responders, or who developed low or adequate quantitative Ig spike antibodies using the Roche Elecsys semi-quantitative spike Ab Ig assay during usual clinical care.

Demographic and clinical characteristics will be summarized by vaccine response level using medians with interquartile ranges (IQR) for continuous variables and frequencies with proportions for categorical variables. Statistical comparisons between vaccine response level will be performed using Pearson's chi-square or Fisher exact tests for categorical variables and Wilcoxon rank-sum test for continuous variables, using an adequate response as the comparator.

Incidence rates and 95% confidence intervals of COVID vaccine adequate response, non-response and low response to COVID vaccines will be estimated using univariate Poisson regression. Incidence rates will be obtained both overall and by vaccine type. The incidence rate is defined as the number of events during follow-up divided by person-time at risk of the event. Estimating incidence rates with Poisson regression allows the use of all person-time time at risk of the outcome, even with differential lengths of follow-up between groups.

Objective #2: Rate of decline in antibody levels over time by HIV status, vaccine type, and baseline CD4 count after initial vaccination

Rates and 95% confidence intervals of antibody levels decay will be estimated among individuals with at least two antibody measurements. Univariate linear regression, will be employed, using the continuous antibody level as the dependent variable, and timing of tests as

the dependent variable. Robust variance estimator will be used to account for repeated measures. Rates of decay will be produced overall, and stratified by HIV status, vaccine type and baseline CD4 cell count.

ANALYSIS OF SECONDARY OBJECTIVES

Objective #3: COVID-19 boosters given

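### Objective 1 sets no latest test date, no index-test rule and no adjustment for time since last dose, so waned titers can be counted as low or non-response

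*Combined protocol and SAP*

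**What the plan says.** - **Eligibility (Section 5, Inclusion Criteria).** Criterion 3 reads "Fully vaccinated against SARS-CoV-2 virus, implemented as 21 days after the second Pfizer or Moderna injections", with the same 21 days after the single J&J dose. Criterion 4 asks that the patient "Received a Roche SARS-CoV-2 Semi-Quant Spike Ig AB test after full vaccination as usual clinical care". The Synopsis also gives a three-week minimum. None of these sets a maximum.
- **Follow-up (Section 6, Overview).** "These individuals will be followed from vaccination until study end".
- **Categories (Section 6, Study Endpoints).** Non-response, low response and adequate response are titer bands with cutoffs at about 50 and 250 U/mL. No day or window is attached. Low and non-responders "were offered optional booster vaccinations with subsequent antibody response measurement post vaccination as standard of care".
- **Covariates (Section 6).** "Covariates of interest include: age, sex, race, ethnicity, HIV status, region, payer, immunosuppressive conditions, CD4 cell count, comorbid conditions, BMI". Time from last dose to test is not listed.
- **Objective 1 analysis (Section 7).** Characteristics are compared across response levels with unadjusted tests. Rates of each response level come from univariate Poisson regression, overall and by vaccine type. "The incidence rate is defined as the number of events during follow-up divided by person-time at risk of the event".
- **Decay (Section 7, Objective 2).** "Rates and 95% confidence intervals of antibody levels decay will be estimated among individuals with at least two antibody measurements".
- **Sensitivity analyses (Section 7).** Marked as not applicable.
- **Post-booster response.** In the Synopsis, "vaccination and antibody response will be characterized at least 3 weeks after the booster is received". Section 7, Objective 3, sets the minimum at two weeks.

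**The concern.** Titers fall after vaccination, and Objective 2 exists to measure that fall. The Background separates people who never developed a protective response from people who did not sustain one. Objective 1 merges the two, because its categories depend on the titer alone and the test may have been taken at any time from day 21 to study end.

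A low titer months after the last dose may well matter for booster timing, but it is not evidence that the vaccine failed to elicit a response. Objective 1 is a primary objective. It is to be described by HIV status and related to vaccine type. Testing was part of usual care and only some patients were tested, so nothing in the design equalises test timing between groups. If one group tended to be tested later, it would appear to respond worse.

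Two features add to the problem:

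- With no pre-booster rule, a retest after a booster could be counted as response to the primary series, which pushes the error the other way.
- A person-time rate suits an event that arises over time. Here the outcome is a category read from a test, so the rate depends on length of follow-up even when the share of low responders does not change.

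**Working it through.** The plan states no figure on this point, so there is nothing to reproduce. The check has three parts.

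**1. Do the timing rules bound the test?** The Synopsis gives at least three weeks, criterion 3 gives 21 days, and Objective 3 gives two weeks after vaccination. All are lower bounds. The overview runs follow-up to study end. No section says whether the first, last or highest test counts. Time of test is modelled only in the decay analyses (Objectives 2 and 4), which need at least two measurements and do not feed the Objective 1 categories. A patient with one late test is in Objective 1 and in neither decay analysis.

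**2. How much could timing matter?** This is an illustration. Apart from the 250 and 50 U/mL cutoffs and the day-21 start, every input is an assumption and not from the documents:

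- titers log-normal, log10 SD 0.4, 0.5 or 0.6;
- half-life (HL) 60, 90 or 120 days;
- day-21 median M of 1,000 or 2,500 U/mL.

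The share at or below cutoff c on day d is

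Φ( [log10 c − log10 M + ((d − 21)/HL) × log10 2] / SD ).

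Worked case with c = 250, M = 1,000, SD 0.5, HL 90:

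- Day 60: (2.398 − 3 + (39/90) × 0.301)/0.5 = −0.943, so 17.3%.
- Day 120: (2.398 − 3 + (99/90) × 0.301)/0.5 = −0.542, so 29.4%.
- Difference with identical response: 29.4 − 17.3 = 12.1 points.

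Ranges over all nine SD and half-life combinations, at or below 250 U/mL:

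| | M = 1,000 | M = 2,500 |
|---|---|---|
| Day 21 | 7% to 16% | 1% to 5% |
| Day 180 | 31% to 69% | 7% to 37% |
| Day 120 minus day 60 | 8 to 24 points | 2 to 11 points |

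For non-response alone (c = 50), the same formula gives about 1% to 20% at day 180 for M = 1,000 and 0.1% to 7% for M = 2,500. Most of the shift is therefore into the low-response band.

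Would a window be enough by itself? With SD 0.5 and tests spread from day 21 to day 90, the share at or below 250 still moves from 11% to between 20% (HL 120) and 30% (HL 60) for M = 1,000. For M = 2,500 it moves from 2% to between 5% and 10%. A window reduces the timing effect but does not remove it.

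**3. Does person-time correct for timing?** No. It rescales the count and leaves the classification unchanged. Suppose 20% test low in each of two groups:

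- mean 3 months at risk: 0.20/(3/12) × 100 = 80 per 100 person-years;
- mean 6 months at risk: 0.20/(6/12) × 100 = 40 per 100 person-years.

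The proportions are equal and the rates differ twofold.

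**Related inconsistency.** A post-booster test on days 14 to 20 is eligible under Objective 3 and not under the Synopsis.

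**The case against.** The best defence is that the study asks whether current titers can guide booster timing, and that the cutoffs are presented as protection thresholds against Delta. For that question a waned titer is informative, and the fault lies mainly in calling it response. This is fair as far as it goes, but Objective 1 does call it vaccine response, and a contrast by HIV status or vaccine type cannot be read that way when test timing is uncontrolled.

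Other points, and what stands of each:

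- *The endpoint text ties the adequate threshold to the last vaccination in a series.* True. That anchors the category to a dose but gives no window after it.
- *Boosted patients have their own Objectives 3 and 4, so Objective 1 is implicitly about the primary series.* A reasonable reading, but no sentence keeps post-booster tests out of Objective 1.
- *Nothing in Objective 1 is adjusted, so omitting one covariate shows little, and the study is descriptive.* A descriptive proportion still needs a defined measurement time. It is also true that adjusting for time alone leaves age and CD4 count unadjusted.
- *No HIV-stratified rate is spelled out.* Correct for the Poisson step. HIV status is nonetheless in the objective and its analysis heading, and rates by vaccine type are planned.
- *Counting a later fall below a cutoff as an event is an inference.* It is. The plan does not say when person-time stops, so the text permits that reading without stating it.
- *Separate analysis specifications may hold an index-test rule.* Section 9 says such specifications are developed. They are not in these documents and cannot be relied on here.
- *The size rests on assumptions.* It does, and it is presented only as an illustration.

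**Conclusion.** The concern holds. Followed exactly, the plan can classify a waned titer as low or non-response, can admit a post-booster titer to primary-series response, and reports a test-defined category as a rate that shifts with length of follow-up.

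The size in this study cannot be derived, because the documents give neither test dates nor titer distributions. The 8 to 24 point and 2 to 11 point differences hold only under log-normal titers, exponential decay, the stated SDs, half-lives and medians, and test times of day 60 against day 120. If groups were tested at similar times since the last dose, the between-group bias vanishes, although the overall shares would still mix non-response with waning. The plan should be changed on this point, since a primary objective is affected and the remedy uses data already held.

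**What to change.** 1. Define primary-series response from one index test per patient: the first test before any booster, within a pre-specified window after the last primary dose. Choose the window from test dates alone, before titers are examined for this analysis. Some results have already been acted on in clinic, so record who set the window and what they had seen.
2. Report the proportion in each response category with a 95% confidence interval, in place of the person-time incidence rates.
3. In comparisons by HIV status and vaccine type, adjust for time since last dose or standardise the proportions to one common day.
4. Show the distribution of time from last dose to index test by group.
5. Keep late-tested patients in a time-standardised analysis of everyone with a pre-booster test, and use later tests for decay.
6. Reconcile the two-week and three-week post-booster intervals to one stated minimum.

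The cost is analysis-plan wording, a date filter and one simple time-adjusted model, with no new data collection. There are two drawbacks. Patients first tested late leave the windowed analysis, and the number lost is unknown because the documents give no count of tested patients. The adjusted model also depends on an assumed shape for the effect of time.

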The AHF Midtown Manhattan Healthcare Center is part of the AIDS Healthcare Foundation (AHF) network. AHF is a global nonprofit organization providing cutting-edge medicine and advocacy to over 1,500,000 people in 45 countries. Currently, the AHF Midtown Manhattan Healthcare Center provides care for 993 HIV-positive and 946 HIV-negative individuals who have had at least one clinical contact in the past 24 months.

Among HIV-positive patients active in care at AHF Midtown Manhattan Healthcare Center, the median age is 53 years (IQR: 38, 61); 95% are men, 22% are Black and 19% are Hispanic. Most HIV-positive patients have their healthcare covered by commercial insurance (52%), Medicaid (29%), Medicare (16%) and/or ADAP/Ryan White (14%). The median follow-up time at AHF Midtown Manhattan Healthcare Center is 7.3 years (IQR: 2.3, 8.6); 14% have at least 10 years of follow-up.

Among HIV-negative patients active in care at AHF Midtown Manhattan Healthcare Center, the median age is 44 years (34, 56); 91% are men, 11% are Black and 16% are Hispanic. Most have their healthcare covered by commercial insurance (70%) or Medicaid (18%). The median follow-up time at AHF Midtown Manhattan Healthcare Center is 4.9 years (IQR: 1.6, 7.9); 8% have at least 10 years of follow-up.

DESCRIPTION OF THE DATABASE AND PREPARATION OF ANALYTICAL FILES

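### No HIV-positive versus HIV-negative result is adjusted for age or any other listed covariate, and Objective #1 has no planned rate by HIV status

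*Combined protocol and SAP*

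**What the plan says.** - **Covariates (Section 6, Study Covariates).** "Covariates of interest include: age, sex, race, ethnicity, HIV status, region, payer, immunosuppressive conditions, CD4 cell count, comorbid conditions, BMI". The section adds that they come from the health record. It gives them no role in a model.
- **Objective #1 (Section 7).** Adequate response, "non-response and low response to COVID vaccines will be estimated using univariate Poisson regression". On strata: "Incidence rates will be obtained both overall and by vaccine type". Patient characteristics are also compared between response levels by chi-square, Fisher and Wilcoxon tests, with adequate responders as the comparator.
- **Objective #2 (Section 7).** Univariate linear regression of antibody level on test timing. "Rates of decay will be produced overall, and stratified by HIV status, vaccine type and baseline CD4 cell count". Objective #4 repeats this after a booster, with booster type in place of vaccine type.
- **Sensitivity analyses (Section 7).** Not applicable, according to the plan. No multivariable model, matching, weighting or standardisation appears anywhere.
- **Source population (Section 4).** The clinic "provides care for 993 HIV-positive and 946 HIV-negative individuals who have had at least one clinical contact in the past 24 months". For HIV-positive patients, "the median age is 53 years (IQR: 38, 61); 95% are men, 22% are Black and 19% are Hispanic"; for HIV-negative patients, "the median age is 44 years (34, 56); 91% are men, 11% are Black and 16% are Hispanic".

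**The concern.** The study title asks whether titres should guide boosters whatever the patient's HIV status, immune suppression or age. The rationale in Section 2 points to a lack of data comparing people with and without HIV. Section 6 names HIV-positive versus HIV-negative as a subgroup of interest. Answering such a question means separating HIV from age, and no planned analysis does that. If response or decay depends on age and the HIV groups differ in age, the crude group results mix the two. An apparent HIV difference could then be partly or wholly due to age, or a real one could be masked. Stratifying by HIV status and vaccine type does not deal with age.

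There is a second gap. Objective #1 is stated by HIV status, but the rates planned for it are not broken down that way.

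**Working it through.** The plan gives no sample size, power, effect size or age effect, so it has no figure of its own to reproduce. The check has three steps.

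**1. Age gap in the source groups (Section 4).**
- Medians: 53 − 44 = 9 years. Lower quartiles: 38 − 34 = 4. Upper quartiles: 61 − 56 = 5.
- Mean estimated as (Q1 + median + Q3)/3: (38 + 53 + 61)/3 = 50.7 and (34 + 44 + 56)/3 = 44.7, a gap of 6.0 years.
- SD estimated as IQR/1.349: 23/1.349 = 17.0 and 22/1.349 = 16.3; root mean square 16.7. Standardised difference: 6/16.7 = 0.36 on estimated means, 9/16.7 = 0.54 on medians.
- Other characteristics, using (a − b)/√[(a(1 − a) + b(1 − b))/2]: Black 22% vs 11%, 0.11/0.367 = 0.30. By the same formula, commercial insurance 52% vs 70% gives −0.38, Medicaid 29% vs 18% gives 0.26, and men 95% vs 91% gives 0.16.

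**2. Apparent HIV effect on non- or low response when the true effect is zero.** The cut at age 50 and the response rates are assumptions.
- Share under 50 by linear interpolation. HIV-positive: 25% + 25% × (50 − 38)/(53 − 38) = 45%, so 55% are 50 or over. HIV-negative: 50% + 25% × (50 − 44)/(56 − 44) = 62.5%, so 37.5% are 50 or over.
- Assumed 10% under 50 and 20% from 50: 0.10 + 0.10 × 0.55 = 15.5%; 0.10 + 0.10 × 0.375 = 13.75%. Ratio 1.13, difference 1.75 points.
- Assumed 5% and 25%: 0.05 + 0.20 × 0.55 = 16.0%; 0.05 + 0.20 × 0.375 = 12.5%. Ratio 1.28, difference 3.5 points.

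**3. Apparent HIV effect on titre when the true effect is zero.** Ages were simulated from the stated quartiles with 993 and 946 patients. Assumptions: ages 18 to 85, residual SD 1 on the log scale, and a titre fall of 5%, 10% or 20% per decade of age.
- Crude HIV-positive/HIV-negative geometric mean ratio: 0.978, 0.955 and 0.902. With age in the model it is 1.00 each time.
- Cross-check: with ages uniform between the quartiles and the assumed limits, mean ages are (28 + 45.5 + 57 + 73)/4 = 50.9 and (26 + 39 + 50 + 70.5)/4 = 46.4, a gap of 4.5 years. Then 0.95^0.45 = 0.977, 0.90^0.45 = 0.954 and 0.80^0.45 = 0.904, which agrees.
- A wider gap gives a larger distortion: 0.97, 0.94 and 0.87 at 6 years; 0.95, 0.91 and 0.82 at 9 years.

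**The case against.** The strongest reply is that the study is descriptive. Objectives #1 to #4 set out to describe and #5 to record. The only comparator Section 7 names is adequate response. Decay rates are produced per stratum, and no HIV difference is estimated or tested as such. Crude stratum rates are a legitimate descriptive result. This stands as a defence of reporting them. It does not cover the comparison that the title, rationale and subgroup wording invite, and the plan nowhere says that HIV differences should not be interpreted.

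Four stronger readings are tempting, and the documents do not support them:

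- **The analysed groups differ by 9 years.** The ages describe all active clinic patients. The study cohort is the vaccinated and antibody-tested subset, whose ages are not given, and 9 years is larger than the gap at either quartile.
- **Vaccine type is ignored, or its mix confounds HIV.** Vaccine type is a planned stratifier for response and decay. If it is crossed with HIV status, HIV results fall within vaccine type. No vaccine or comorbidity distribution by HIV status is given. Assumed J&J shares of 15% and 5%, with non- or low response of 60% for J&J and 8% for mRNA, would give 15.8% vs 10.6% (ratio 1.49), but none of those four inputs comes from the documents.
- **The covariates are not used at all.** HIV status and CD4 count are strata in Objectives #2 and #4, and others may appear in the descriptive tables and one-at-a-time tests by response level.
- **Differences will be read as HIV effects.** That predicts what readers will do. The documents support only that they could be.

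**Conclusion.** The point holds in limited form. No planned HIV-positive versus HIV-negative result is adjusted for age or any other listed covariate, the crossing of HIV and vaccine-type strata is unstated, and Objective #1 lacks the breakdown by HIV status that it names. The source groups differ in age, race and payer.

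The size of any age distortion cannot be fixed from the documents. Under the assumptions in the working, the crude ratio of non- or low response is about 1.13 to 1.28, and the crude titre ratio is 0.98 to 0.90 in the simulation, with no HIV effect at all. These figures assume that the tested cohort has the clinic's age pattern and that response worsens with age as supposed. With a smaller gap the distortion shrinks; with a reversed gap it changes sign and could mask a real HIV difference. The plan should be changed before analysis, but the gap does not invalidate the descriptive results.

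**What to change.** In Section 7:

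- Keep the crude results, label them descriptive, and state whether HIV and vaccine-type strata are crossed.
- Add response by HIV status to Objective #1, and a baseline table split by HIV status.
- For Objectives #1, #2 and #4, add one HIV-positive versus HIV-negative contrast with 95% CI, adjusted for age (continuous), sex, and vaccine or booster type.
- For decay, include an HIV-by-time term and the matching covariate-by-time terms, at least for age and vaccine or booster type. Main effects alone adjust the level and leave the slope comparison confounded.
- Add comorbidity where numbers allow. Put immunosuppressive condition only in a secondary model, and leave CD4 count out of the main one, because both may lie on the pathway from HIV to response and adjusting for them could remove part of the difference of interest.
- Base any statement about HIV on the adjusted contrast.

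The cost is plan wording and a few models on variables that, vaccine type included, the plan already intends to obtain. Intervals may be slightly wider and sparse categories may need collapsing. The plan gives no count of tested patients or of those with two or more tests, so the size of model the data will bear must be checked first.
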